4.1.2 Secondary outcome measures

- Number of HDU/ICU admissions
- Length of stay in HDU/ICU
- Total length of stay in hospital
- Postoperative complications, graded using the Clavien-Dindo classification
- Re-interventions
- Patient acceptability, as determined by the patient questionnaire and structured interviews, and focus groups
- The number of patients failing to complete SensiumVitals[®] monitoring for 5-days, or length of hospital stay (and reasons)
- Nursing acceptability, as determined by the Modified System Usability Score and structured interviews

4.2 Research tools (please see Appendices)

4.2.1 Patient questionnaire

A simple three-question questionnaire will be administered to all 'patched' patients, on discharge from hospital. This will primarily assess the comfort of the patch to wear, and whether or not the patient felt safer wearing the patch. Further feedback shall be encouraged with a white box question.

4.2.2 Modified System Usability Score

Nursing staff satisfaction shall be quantified using the system usability score (8), a well-recognised, robust and versatile tool for obtaining a subjective rating of a product by the user (9). Further feedback shall be encouraged with a white box question.

4.2.3 Topic guide for patient interviews

On discharge from hospital, every 'patched' patient will be invited to participate in a structured interview with the researcher. The purpose of these interviews is to obtain information about the patients' opinions, beliefs, experiences and feelings in regard to the way they have been monitored during their hospital stay. Patients who did not complete the SensiumVitals[®] monitoring trial will be included to understand their reasoning and choices.

The topic guide encourages open and neutral questions. The use of a topic guide will assist with comparability between interviews at the analysis stage. It is anticipated that each interview will last approximately 10-30 minutes.

4.2.4 Topic guide for nursing staff interviews

At the end of the study period, members of the nursing staff will be invited to participate in a structured interview with the researcher. Participants will be recruited using purposive sampling. Three members of the nursing staff from each of the four participating wards will be interviewed. It is anticipated that each interview will last approximately 10-30 minutes.

Interviews will be recorded with the interviewee's consent, transcribed verbatim, anonymised and uploaded to NVivo 10.

4.2.5 Topic guide for focus groups

It is anticipated that two focus groups will be held, which will include approximately 6 patients. Each focus group will last 1 hour, and be attended by at least one member of the research team, one facilitator and a PPI (patient and public involvement) representative.

The first focus group will have two aims:

- To allow further information gathering about patient experience of the patch, to add to data already gleaned from one-to-one structured interviews.
- To gain the patient's perspective of the study itself: its conduct and progress. This will help to optimise the study protocol to improve the patients' experience of being involved in the research.

The second focus group will have two aims:

- To feed back the results of the study to the participants
- To gain patients' perspective about how to maximise the impact of the results, including feedback on lay summaries.

5. Trial subject selection

5.1.1 Inclusion criteria

All patients admitted to the participating surgical wards, most of whom will have undergone/be undergoing major surgery:

- emergency and elective admissions
- male and female patients
- benign or malignant diseases
- all ages >16 years and comorbidities
- includes pregnant and breastfeeding women

5.1.2 Exclusion criteria

- those who do not consent
- allergy to adhesives on electrodes
- cardiac pacemaker in situ

5.1.3 Statistical analysis

Analysis will be on an intention-to-treat basis. Each of the outcome measures will be summarised by intervention or control group using appropriate descriptive statistics. As this is a feasibility study no formal comparison between the study arms will be undertaken. Subgroup analysis will be performed, specifically to determine any differences between lowand high-risk patients.

Framework analysis will be used for analysis of the qualitative data. A thematic framework will be developed and applied to all the transcripts. The data will be summarised in matrix displays to facilitate comparison between participants.

5.1.4 Concurrent clinical trials

Patients will be screened for inclusion in other clinical trials. Providing there is no conflict, patients may be included in this and other trials.

5.2 Recruitment, consent and randomisation processes

5.2.1 Recruitment

All patients admitted to the participating adult general surgical wards will be eligible to participate in the trial. The patient will be approached to join the trial as soon as possible after admission to the ward.

Patients will be initially approached by a member of the nursing staff, or one of the researchers. A verbal explanation of the trial and Patient Information Sheet will be provided for the patient to consider. This will include detailed information about the rationale, design and implications of the study. Patients will be allowed a period for consideration, and discussion with relatives if required, before signing the consent form.

An orange notice will be placed in the front of the patient's notes to alert other healthcare providers that they are included in the trial, and to act as a reminder of the patients' allocation for reference should they be moved off one of the participating wards, or return to a participating ward from HDU/ICU.

5.2.2 Consent

Assenting patients will be formally assessed for eligibility and invited to provide informed, written consent. The right of the patient to refuse consent without giving reasons will be respected. Further, the patient will remain free to withdraw from the study at any time without giving reasons and without prejudicing any further treatment. A copy of the consent will be given to the patient, filed in the Trial Master File and the hospital notes. The written consent will be taken by a healthcare professional, who has signed the staff delegation log. The process of obtaining written consent will be clearly documented in the patient's medical notes.

5.2.3 Randomisation

Randomisation of bays and side rooms as either intervention or control will be performed prior to patient recruitment by the Leeds Clinical Trials Unit. Whilst the allocation of patients to their bed on the ward is not truly a random process, the bed managers are removed from both the study and ward-based care, thus minimising selection bias.

5.2.4 Blinding

Blinding is not applicable for this study.

5.2.5 Patients who withdraw consent

In line with usual clinical care, cessation or alteration of regimens at any time will be at the discretion of attending clinicians or the participants themselves. The PI, or delegate, will make every effort to ensure that the specific wishes of any participant who wishes to withdraw consent for further involvement in the study are defined and documented. All patients will be able to withdraw from the study at any time, and will be reassured that this will not influence their subsequent standard of care.

5.2.6 Definition for the end of study

The 'end of trial' will be defined as the last recruited patient's date of discharge. At this point, the 'end of trial notification' will be submitted to the relevant ethics committee.

6. Product information

6.1 SensiumVitals[®] remote monitoring system

The SensiumVitals[®] Wireless Monitoring Application System is intended for use by health care professionals for routine monitoring of patient physiological parameters to include, heart rate, respiratory rate and axillary temperature, in a hospital setting. The patient-facing device is a CE-marked patch which will be used within its market-intended purpose. Data is transmitted wirelessly over medical grade radio frequency (915/866 MHz) to hospital secured server. Data transmitted over the air has no patient identifiers.

All data are stored and retained on the hospital network. The SensiumVitals[®] system utilizes the hospital's Active Directory as its authentication mechanism for handling user logins to the application and access to data. Active Directory provides centralized management of the staff who will be using the application in the hospital.

The SensiumVitals[®] system therefore inherits all the hospital security procedures and data backup policies, to ensure data access and servers are secured. Communication to the SensiumVitals[®] Windows client is done using an Advanced Encryption Standard Secure Sockets Layer (SSL) certificate with encryption. Data is backed up frequently as per hospital procedures. In case of system failure, the patch will automatically buffer data for up to three hours continuously until the hospital server is back online.

7.Trial schedule

7.1 Study timeline

May 2016 – August 2016: Set-up: 3-months to include study design, protocol writing, regulatory approvals (Ethics and R&D), and staff training.

August 2016 – May 2017: Patient recruitment: recruitment of 500 patients to either SensiumVitals[®] + NEWS monitoring or NEWS monitoring alone. Data collection including time to treatment of sepsis, Level II/III care utilisation and patient/staff satisfaction surveys. Qualitative analyses using focus groups and with the help of the NIHR HTC in Colorectal Therapies.

May 2017 – August 2017: Data analysis and dissemination, writing of manuscript for publication, and presentation to clinical and patient and public forums.

7.2 Project milestones

May 2016: Completion of study, including regulatory approvals

August 2016: Patient recruitment starts

May 2017: Completion of patient recruitment

August 2017: Results dissemination and publication. End of study

8. Reporting of adverse events

8.1 Defining adverse events (AE)

An AE is any untoward medical occurrence in a patient during or following administration of an investigational product or procedure and which does not necessarily have a causal relationship with treatment. An AE can therefore be any unfavourable and unintended sign (including an abnormal laboratory finding), symptom, or disease temporarily associated with the use of the product, whether or not considered related to the trial product.

8.2 Defining serious adverse events (SAEs)

A SAE is defined in general as an untoward (unfavourable) event, which:

• is fatal. Death may occur as a result of the basic disease process. Nevertheless, all deaths occurring within 30 days of the last administration of the study agent must be treated as an SAE and reported as such. All deaths which may be considered as related to the trial agent, regardless of the interval, must be treated as a SAE and reported as such.

- is life-threatening
- requires or prolongs hospitalization
- results in persistent or significant disability or incapacity
- is a congenital anomaly or a birth defect, or
- may jeopardise the patient and may require medical or surgical intervention to prevent one of the outcomes listed above

Any other significant clinical event, not falling into any of the criteria above, but which in the opinion of the investigator requires reporting.

8.3 Reporting AEs

AEs will be collected for all patients and will be evaluated for duration and intensity according to the NCRI Common Toxicity Criteria.

Safety will be assessed by review of adverse events from the time of registration into trial to 30 days post-operatively.

Information about AEs, whether volunteered by the patient, discovered by the investigator questioning or detected through physical examination, laboratory test or other investigation will be collected and recorded.

A copy of all reported AEs will be sent to the sponsor if requested.

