2.2 Vital signs monitoring

2.2.1 National Early Warning Score

The current standard of care for monitoring patients in the postoperative period is to record their vital signs (blood pressure, pulse, temperature, respiratory rate) using the National Early Warning Score (NEWS). Derangements in individual vital signs are scored according to their magnitude, and the scores summated to reflect the patient's overall condition. A higher score indicates patient deterioration, the need for escalation of care, and is linked to an increased chance of death.

The NEWS is calculated intermittently, at intervals directed by the patient's condition. Typically, in the postoperative period NEWS will be calculated half hourly for the first few hours, and if the patient remains stable the frequency will decrease to 2-hourly and then 4hourly, until the patient is ready for discharge when the NEWS may be recorded only twice a day.

Although NEWS has proven benefit, it suffers from several drawbacks. A 2012 study evaluated early warning scores in patients 48 hours before an adverse event (5). 81% of

patients had a score indicative of deterioration, but recordings were 'mostly incomplete' with respiratory rate documented in 'only 30% to 66%'.

NEWS relies on manual observations, is time-consuming, and open to user interpretation. Vital signs are taken at predetermined intervals (typically 4-hourly), with patient deterioration possible between recordings. It has been suggested that the gap between observations is one of the primary failings of the NEWS system (6).

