2.3 Rationale for the proposed study

It is hypothesised that the SensiumVitals[®] system, as an adjunct to standard NEWS monitoring, will allow earlier detection of postoperative complications. This should reduce morbidity, which in turn should result in a decreased need for high dependency/intensive care.

3. Study objectives

To evaluate the safety, efficacy and acceptability of a new, wearable, remote monitoring system (SensiumVitals[®]) for patients admitted to surgical wards, as compared to standard monitoring with the National Early Warning Score system alone.

4. Study design

This is a single-centre feasibility study. Patients will be selected on the basis they are admitted to one of four general surgery wards. We will include 500 patients, most of whom will undergo a surgical procedure during their hospital stay.

When patients are admitted to a general surgery ward, they are allocated a bed by a team of 'bed managers' based on clinical need and availability. Each of the participating general surgery wards is divided into 'bays' of four or six beds, and 'side rooms' which contain only one bed. Prior to the commencement of the study, each bay and side room on each of the participating wards will be randomly allocated to receive 'patched' patients, or NEWS-monitored controls. The randomisation of bays will be balanced for ward type, taking account of patient gender and surgical subspecialty.

Patients will be identified as potentially eligible to participate in the study and approached on admission to the surgical wards. At this point they will be given further information in the form of a patient information sheet regarding the study. Following a period of consideration, if they have decided to participate in the study they will receive the appropriate monitoring. Information will also be collected regarding the number of patients who agree to take part in the study, those who do not and the reason for not taking part.

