For the duration of the study, when a patient is admitted to one of the participating wards, they will be allocated to one of the two study arms according to the bay or side room to which they are allocated by the bed managers. The bed managers are removed from ward-based care and the allocation of a patient to a particular bed is 'random' and avoids selection bias. Eligible patients in the 'patch' bays/side rooms will receive a patch and standard NEWS monitoring. Patients in the 'control' bays/side rooms will receive standard NEWS monitoring alone.

All usual nursing and medical care are permitted within both arms of the trial. This includes fluid balance monitoring, neurological observations, etc.

Roughly half of the patients (250) will be offered the new system. The devices are designed to be lightweight and unobtrusive, with a battery life of 5 days. Patients will be expected to wear the device for the duration of their hospital admission. The device will monitor the patient's heart rate, respiratory rate and temperature continuously, and send this information every two minutes to a mobile device carried by the patient's nurse. The information is also available on the ward computer monitors.

The patients will remain in their allocated study arm for the duration of their hospital stay. If a 'patched' patient is moved to a critical care bed during their admission, the SensiumVitals[®] monitoring will be temporarily suspended pending reinstatement depending on the ward bed to which they return. Every effort will be made to ensure that patients remain in the study arm to which they were originally allocated, and any non-compliance will be recorded. Analysis will be on an intention-to-treat basis.

Patients' participation in the trial will end when they are discharged from hospital. At this point, 'patched' patients will be invited to complete a questionnaire and /or undertake a structured interview regarding their experiences of wearing the patch. Patients will also be invited to attend one or more focus groups after discharge from hospital. Information regarding the admission will be collected once the patient has left hospital.

The staff nurses will be invited to complete a paper questionnaire in the form of a Modified System Usability Score. They will also be invited to undertake a structured interview regarding their experience of providing the new monitoring system.

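### Open-ended AE sources in 8.1 and 8.3, together with monitoring and questioning that only the patch arm receives, may inflate AE counts in that arm and distort the descriptive safety comparison

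*Protocol*

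**What the plan says.** **What counts as an AE.** Section 8.1: "An AE can therefore be any unfavourable and unintended sign (including an abnormal laboratory finding), symptom, or disease". The event need not be related to the product. The same sentence ties the event to use of the product, which has no clear meaning for a control patient.

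**Who and from where.** Section 8.3: "AEs will be collected for all patients and will be evaluated for duration and intensity". The sources are open: "whether volunteered by the patient, discovered by the investigator questioning or detected through physical examination, laboratory test or other investigation". Nothing limits them to sources that both arms share, and nothing says whether patch readings or interview answers count. Safety is to be assessed by reviewing these events up to 30 days after the operation.

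**What each arm receives.** Under section 4, patch patients have heart rate, respiratory rate and temperature sent every two minutes in addition to NEWS, and controls have NEWS alone. Section 2.2.1 describes NEWS: "Vital signs are taken at predetermined intervals (typically 4-hourly), with patient deterioration possible between recordings". On discharge, section 4 adds: "At this point, 'patched' patients will be invited to complete a questionnaire and /or undertake a structured interview". Sections 4.2.1 and 4.2.3 confirm that both instruments are for patched patients. Section 5.2.4 states that there is no blinding.

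**What is compared.** The objective in section 3 begins "To evaluate the safety, efficacy and acceptability of a new, wearable, remote monitoring system", and the comparator is NEWS alone. Section 5.1.3 summarises each outcome measure by group without formal comparison. Section 4.1.2 lists among those outcomes "Postoperative complications, graded using the Clavien-Dindo classification".

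**The concern.** The two arms are not searched equally for the events that section 8 counts. The protocol's own rationale is that NEWS can miss deterioration between rounds and that the patch finds it earlier. It cannot also be taken for granted that abnormal vital signs will be found equally often in both arms. A short tachycardia or fever between rounds can be seen in a patch patient and leave no trace in a control. The discharge questionnaire has a free-text box, and the interview guide asks about bad things and bother from the patch. No matching contact with controls is described.

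With no formal test planned, readers will take the counts by arm at face value. Part of any excess under the patch could then reflect closer observation rather than harm. A later analysis plan cannot undo this unless the source of each event was recorded when it was collected.

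**Working it through.** The protocol states no expected AE rate, detection rate or sample size calculation, so there is no figure of its own to reproduce. What follows shows the direction and a possible range.

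**1. Intensity of observation (section 4, section 2.2.1).**
- Patch: 24 × 60 / 2 = 720 transmissions per day, plus NEWS.
- Control at 4-hourly rounds: 24 / 4 = 6 sets per day.

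**2. Short vital-sign episodes, equal true rates in both arms.** Assumptions, none from the protocol: an episode of d minutes starts at random between rounds; the patch sees all such episodes; every episode seen is recorded as an AE; a share f of all true AEs are such episodes.
- Chance that a 4-hourly round sees it = d/240: 12.5% (30 min), 25% (60 min), 50% (120 min).
- Share of all AEs missed in controls = f × (1 − d/240).
- Apparent patch-to-control ratio = 1 / (1 − share missed).

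| f | d = 30 min | d = 60 min | d = 120 min |
|---|---|---|---|
| 10% | 8.75% missed, 1.10 | 7.5%, 1.08 | 5%, 1.05 |
| 20% | 17.5%, 1.21 | 15%, 1.18 | 10%, 1.11 |
| 30% | 26.25%, 1.36 | 22.5%, 1.29 | 15%, 1.18 |

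**3. The 4-hour interval is not fixed.** Section 2.2.1 has rounds half-hourly for the first few hours, then 2-hourly, then 4-hourly, and possibly twice daily before discharge. With f = 20%:
- Half-hourly: a 30-minute episode is always seen (30/30 = 1), ratio 1.00.
- 2-hourly: 30 min, 1/(1 − 0.20 × 0.75) = 1.18; 60 min, 1/(1 − 0.20 × 0.50) = 1.11; 120 min, 1.00.
- Twice daily (720 min): 30 min, 1/(1 − 0.20 × (1 − 30/720)) = 1.24; 120 min, 1/(1 − 0.20 × (1 − 120/720)) = 1.20.

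**4. Cross-check with overall detection rates.** Take 250 per arm (section 4) and a true AE rate of 35% in both arms. That rate is an assumption, midway in the 30% to 40% complication rate that section 2.1 gives for major abdominal procedures. Observed rate = true rate × detection probability (also assumed). The standard error uses the normal approximation and ignores clustering by bay.

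| Detection, control v patch | Observed | Difference (points) | Ratio | SE (points) |
|---|---|---|---|---|
| 80% v 80% | 28.0% v 28.0% | 0 | 1.00 | 4.0 |
| 80% v 85% | 28.0% v 29.75% | +1.75 | 1.06 | 4.1 |
| 70% v 90% | 24.5% v 31.5% | +7.0 | 1.29 | 4.0 |
| 60% v 90% | 21.0% v 31.5% | +10.5 | 1.50 | 3.9 |

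Over true rates of 30% to 40%, the spurious difference runs from 0.30 × (0.85 − 0.80) = +1.5 points to 0.40 × (0.90 − 0.60) = +12.0 points. The low end is well within sampling noise and the high end is not.

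**5. Focus groups.** Section 4.2.5 plans two groups and about 6 patients, so 6 to 12 people: 6/250 = 2.4% to 12/250 = 4.8% of patched patients. They are held after discharge and could fall outside the AE window. They add next to nothing.

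**The case against.** The best defence is that section 8.3 is generic AE wording. It names neither the patch trace nor the questionnaire or interview. Section 8.1 opens with an untoward medical occurrence, and nothing says that a brief reading or an alert must be logged as one. The questionnaire covers comfort and feeling safer, the interviews seek experience and opinion, and the qualitative data go to framework analysis with no stated link to the AE form. AEs are not among the outcomes in section 4.1, so no by-arm AE table is specified, and its layout could properly sit in an analysis plan that is not shown. SAEs are less exposed, since they are collected to discharge in both arms under seriousness criteria.

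Much of this stands, and it limits the claim. It does not remove it. Section 3 makes safety against NEWS an objective and section 8.3 assesses safety from these events. The wording admits signs found by questioning or by any investigation, and only one arm has the extra sources.

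Three stronger readings are tempting and are not supported:
- *A harmless patch will appear more harmful.* The size depends on detection rates that the protocol does not give. Patch monitoring may be incomplete (section 4.1.2 counts non-completers) and is suspended in critical care (section 4). Section 2.3 hypothesises less morbidity under the patch, which could offset the effect.
- *The imbalance would set off the safety concern in section 11.1.* The benchmark there is what is normally experienced in this surgery, not the control arm.
- *A patch alert becomes a complication.* No rule makes it one, and Clavien-Dindo grading is already planned. Only the low grades might be affected.

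**Conclusion.** The point holds as a risk of unequal ascertainment. Followed literally, sections 8.1 and 8.3 allow AEs to be found more readily in the patch arm, chiefly through continuous vital signs and to a lesser extent through the discharge questionnaire and interview. AE counts, and possibly low-grade complication counts, may be inflated there relative to controls. The harm is a misleading descriptive safety table, not a false test result, because no test is planned.

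The size cannot be derived from the protocol. Ratios of 1.05 to 1.36 rest on assumed shares of 10% to 30%, episodes of 30 to 120 minutes, full detection and recording under the patch, and rounds fixed at 4 hours. More frequent rounds shrink the ratio, in some cases to 1.00, and less frequent rounds enlarge it.

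**What to change.** 1. In section 8.3, add a source-of-detection field to the AE form: routine record, questioning common to both arms, patch only, or discharge questionnaire or interview. The form is not shown. If it already has such a field, only the wording is needed.
2. In sections 8.3 and 5.1.3, base any by-arm AE summary on events ascertained the same way in both arms, that is, from the routine hospital record and from questioning common to both.
3. List vital-sign abnormalities seen only on the patch separately, unless they led to a recorded diagnosis, treatment, re-intervention, HDU/ICU admission or death.
4. Keep device-related harms, such as patch-site skin reactions, in the safety results whatever their source, in a patch-arm device-harm table. Controls wear no patch, so these are real device effects. Filing them as experience data because they came up at interview could hide harm.

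The cost is protocol wording and one field on a form, with no new visits or staff. The small downside is that some minor patch-only signs leave the between-arm comparison, though they are still reported. SAE reporting is unchanged.
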